13.6.3. Safety

Clinically Relevant Haemolysis

 • Clinically relevant haemolysis is defined as: a decrease in haemoglobin of $\geq 30\%$ or >30 g/L (>3 g/dL) from baseline; or, an overall drop in haemoglobin below 60 g/L (6.0 g/dL) at any visit after the first dose of study medication. • If a subject has any missing post-baseline haemoglobin data up to Study Day 17, the primary endpoint will be set to missing. • A subject will be classified as not having haemolysis at any visit if they do not meet the above haemoglobin criteria and no visits are missing up to Study Day X. • See Section 13.7.2.3 for further handling of missing data.

ECG Parameters
RR Interval 
 • ECGs are manually read, the RR value preceding the measurement QT interval should be a collected value so no derivation is required.
Corrected QT Intervals 
 • QTcF will be derived at the site and entered into the eCRF.

Adverse Events

 • All AEs reported up to and including the Day 180 visit following enrolment of a subject into the study will be documented. • These will be recorded and coded using the current version of Medical Dictionary for Regulatory Activities (MedDRA). All terms applied will be reviewed by a GSK physician prior to unblinding. If any malaria related coded terms are considered to have lost useful information in the coding step (e.g., if a verbatim term of 'Plasmodium vivax malaria' is mapped to 'malaria'), he/she will recommend a study-specific code, which will be documented. The process will be completed prior to study unblinding. • Treatment emergent AEs are defined as AEs with an onset date and time on or after that of the start of first dose of study medication (including CQ). • AEs with entirely missing or unknown start dates will be assumed to be treatment emergent for reporting. AEs where the start date is equal to that of study medication, but where the start time is unknown will also be assumed to be treatment emergent. AEs with missing end dates are not anticipated to affect reporting. • If the grade/intensity is missing for an AE, it will be considered severe/Grade 3 if an AE, or Grade 4 if an SAE and the subject is alive, or Grade 5 if an SAE and the subject dies (i.e. the highest intensity possible) for the summary of AEs by maximum intensity. • See Section 13.7.2 for more information on missing and partial dates. • Common AEs are those occurring in $\geq 5\%$ of subjects in any treatment group. • The occurrence of malaria and any associated signs and symptoms are recorded as Disease Related Events (DREs) and will not be classified as AEs. • The GSK clinical team will review terms that qualify as haematologically related.

Laboratory Parameters

- If a laboratory value which is expected to have a numeric value for summary purposes, has a non-detectable level reported in the database, where the numeric value is missing, but typically a character value starting with '<x' or '>x' is present, the number of decimal places of x will be used to determine how much to add or subtract in order to impute the corresponding numeric value.
 - Example 1: 2 Decimal Places = '< x' becomes $x - 0.01$
 - Example 2: 1 Decimal Place = '> x' becomes $x + 0.1$
 - Example 3: 0 Decimal Places = '< x' becomes $x - 1$

Absolute differentials and reticulocytes

- If sites provide white blood cell (WBC) differential (i.e., eosinophil, neutrophil, lymphocyte, monocyte and basophil) results as a percentage of total WBCs, these values will be converted to an absolute result (expressed in $10^9/L$, equivalent to G/L) for reporting purposes using the following formula:

$$\text{Absolute differential } (10^9/L) = 0.01x (\text{percentage differential}) \times (\text{WBC in } 10^9/L).$$
- If reticulocytes are reported as a proportion of total red blood cells (RBCs), these values will also be converted to an absolute result (expressed in $10^{12}/L$, equivalent to T/L) using the following formula:

$$\text{Absolute reticulocytes } (10^{12}/L) = (\text{reticulocytes as a proportion}) \times (\text{RBC in } 10^{12}/L).$$

Estimated Glomerular Filtration Rate (eGFR)

- eGFR will be defined using the abbreviated Modification of Diet in Renal Disease formula, when creatinine is in standard unites of $\mu\text{mol}/L$:

$$eGFR (ML/SEC/1.73M^2) = 32788 \times (\text{Creatinine})^{-1.154} \times (\text{Age})^{-0.203} \times (0.742 \text{ if female}) \times (1.210 \text{ if Black}) \times 0.0167$$
- A subject with a race of Black or African American or who has a mixed race including Black or African American will be considered Black for the purpose of the eGFR calculation.

Best Corrected Visual Acuity

- Best corrected visual acuity is assessed individually for each eye. In the eCRF, scores will be recorded as a ratio, for example 6/6, 6/7.5, or 6/9.5. These values will be used to derive a logMAR score for the statistical analysis, where $\text{logMAR} = -1 \times \log_{10}(\text{ratio score})$. Thus, a ratio score of 6/9.5 corresponds to a logMAR score of 0.20.
- logMAR changes from baseline are classified as:
 - no change: <0.12
 - possible change: ≥ 0.12 to <0.3
 - definite change: ≥ 0.3

Vital Signs – Mean Arterial Blood Pressure

- To be calculated (to 1 decimal place) where systolic and diastolic blood pressure are both present at the same timepoint:

[figure not shown]
$$\text{mean arterial blood pressure} = \frac{(\text{systolic blood pressure} + 2(\text{diastolic blood pressure}))}{3}$$

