1.3.2. Benefit Assessment

In the absence of radical cure treatment, a percentage of patients with *P. vivax* malaria will relapse due to the liver being infected with hypnozoites (the dormant form of the parasite). *P. vivax* malaria is most prevalent primarily in Asia, Asia-Pacific and Latin American countries and frequency of relapse rates may impact product use. Relapse rates vary with strain and are difficult to measure due to confounding by re-infection. The WHO have generalized relapse rates in the following countries as: India (15-20%), Indonesia (30%) and South East Asia (50-60%). *P. vivax* can cause a debilitating fever and as it preferentially invades reticulocytes, can also lead to the development of anemia. Repeated relapses are similarly debilitating and may result in further episodes of fever, weight loss, malnutrition and high output heart failure, especially in children. Consequences are loss of work or school days (e.g. 5.4 days school absenteeism per episode) and hospitalization (especially children) due to vomiting, dehydration and anemia (resulting in transfusion).

Due to its long half life, tafenoquine can be administered as a single oral dose and is therefore a more convenient treatment regimen with the potential to improve patient compliance. Improved compliance could also lead to improved clinical outcomes for patients with *P. vivax* malaria by further reducing relapse rates.

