13.7.2.3. Handling of Missing Data for Statistical Analysis

Element	Reporting Detail
Incidence of Haemolysis	
 For the primary analysis only observed data will be used. A sensitivity analysis will be performed where missing haemolysis data before Study Day 17 will be imputed as 'haemolysis=YES'.
Relapse-free efficacy and time to event endpoints	
 For all analyses of the mITT population, subjects will not be excluded from any statistical analyses. From the Day 29 assessment onwards, subjects who have not relapsed but fail to have an evaluable parasite smear within the visit window for every scheduled visit will be excluded from the PP population. See Section 13.6.4 for further details on how missing assessments will be censored.
Derived variables	
 For derived variables, details of how any missing eCRF data will be handled are provided in Section 13.6.

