No.	Population	IDSL / TST ID / Example Shell	Title	Programming Notes	Deliverable
Ophthalmic Assessments					
3.43.	Ophthalmic Safety	SA29	Summary of Keratopathy	If no keratopathy is reported, display should be blank with 'No subjects reported keratopathy displayed'	SAC
3.44.	Ophthalmic Safety	SA30	Summary of Slit Lamp Assessments		SAC
3.45.	Ophthalmic Safety	SA30	Summary of Humphrey Perimetry Assessments		SAC
3.46.	Ophthalmic Safety	SA32	Summary of Colour Perception Assessments		SAC
3.47.	Ophthalmic Safety	SA33	Summary of Best Corrected Visual Acuity Test Scores		SAC
3.48.	Ophthalmic Safety	SA34	Summary of Best Corrected Visual Acuity Classification		SAC
3.49.	Ophthalmic Safety	SA28	Summary of Hyperpigmentation		SAC
3.50.	Ophthalmic Safety	SA28	Summary of Hypopigmentation		SAC
3.51.	Ophthalmic Safety	SA28	Summary of Appearance of Retinal Vessel		SAC
3.52.	Ophthalmic Safety	SA28	Summary of Optic Nerve Pallor		SAC
3.53.	Ophthalmic Safety	SA28	Summary of Confounding Abnormalities		SAC

Safety: Tables					
No.	Population	IDSL / TST ID / Example Shell	Title	Programming Notes	Deliverable
3.54.	Ophthalmic Safety	SA28	Summary of Retinal Changes from Baseline	Exclude baseline rows. Categories will be 'no change', 'questionable change', 'definite change', 'cannot grade'	SAC
Blood Transfusions					
3.55.	Safety	SA38	Summary of Blood Transfusions		SAC

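### The primary haemolysis endpoint uses haemoglobin values alone, so a subject transfused before meeting any criterion, with complete data, counts as a non-event, and no analysis tests this

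*Supplement*

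**What the plan says.** RAP section 13.6.3 sets three haemoglobin criteria for the primary endpoint. Two are measured against the subject's own starting value: "a decrease in haemoglobin of $\geq 30\%$ or >30 g/L (>3 g/dL) from baseline". The third is a fixed floor of 6.0 g/dL, applied at every visit once dosing has begun. On non-events the section states: "A subject will be classified as not having haemolysis at any visit if they do not meet the above haemoglobin criteria". It adds the condition that visits be complete to a cut-off day, which in that line is still a placeholder. The rule for incomplete data reads: "If a subject has any missing post-baseline haemoglobin data up to Study Day 17, the primary endpoint will be set to missing".

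The only sensitivity analysis of the primary endpoint (RAP 7.1.2 and 13.7.2.3, Table 3.2) deals with missing haemoglobin: "missing haemolysis data before Study Day 17 will be imputed as" an event.

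Transfusion appears in RAP Table 4 (section 8.2.3) and as Table 3.55, "Summary of Blood Transfusions", in section 13.14.6. Table 4 marks a summary table only, and Appendix 14 has no listing devoted to transfusions. Sections 7.1.2, 13.6.3 and 13.7.2.3 do not mention transfusion. The protocol's endpoint (sections 2 and 8.3.4.1) is likewise based on haemoglobin only.

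**The concern.** Transfusion raises haemoglobin. Given while a subject is falling but has not yet met a criterion, it can prevent the measured threshold crossing that the endpoint requires. Donor blood can hide a crossing but cannot create one, so the error has one direction: fewer counted events. It bears most on subjects who enter anaemic, because for them the first criterion reached is the fixed floor of 6.0 g/dL.

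The RAP expects few events (7.1.2), so a handful of subjects could matter to the estimate. The post-transfusion values also enter the mean and categorical change-from-baseline summaries as if they were the subject's own recovery.

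The RAP already handles the parallel problem for efficacy. In section 13.6.4, a subject who takes a drug with anti-malarial activity and stays parasite-negative is censored, or is counted as a failure in the missing=failure analyses. The primary safety endpoint has no counterpart.

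**Working it through.** **1. The plan's own figures.** Protocol 8.2.1 gives 95% half-widths of 18%, 25%, 4% and 5%. Using 1.96 × √(p(1−p)/n):
- p = 0.50, n = 30: 17.9%
- p = 0.50, n = 15: 25.3%
- p = 0.08, n = 200: 3.8%
- p = 0.08, n = 100: 5.3%

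The cohort rate is 25/300 = 8.3% (stated 8%). All agree after rounding. They assume a 50-subject deficient subgroup, for which the RAP (2.1) reports recruitment difficulties and drops the estimate.

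**2. Where an event begins.** For baseline B, the first criterion reached lies at max(6.0, 0.70 × B, B − 3) g/dL. Protocol 4.2.1 sets the lowest entry haemoglobin at 7 g/dL, or 8 g/dL for females with 40% to below 70% G6PD activity. Amendment 2 raises it to 8 g/dL for everyone at two Thai centres.

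| Baseline (g/dL) | 0.70 × B | B − 3 | First reached at about |
|---|---|---|---|
| 7.0 | 4.9 | 4.0 | 6.0 |
| 8.0 | 5.6 | 5.0 | 6.0 |
| 8.57 | 6.0 | 5.57 | 6.0 |
| 9.0 | 6.3 | 6.0 | 6.3 |
| 10.0 | 7.0 | 7.0 | 7.0 |
| 12.0 | 8.4 | 9.0 | 9.0 |

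The floor binds below 6.0/0.70 = 8.57 g/dL. There, every value at or above 6.0 g/dL is still a non-event.

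**3. An assumed transfusion range of 6.0-6.9 g/dL.** The documents state no trigger, so this range is illustrative.
- 8.2 to 6.2: fall 2.0 g/dL, 2.0/8.2 = 24.4%. No criterion met.
- 9.0 to 6.2: 2.8/9.0 = 31.1%. Event.
- 9.8 to 6.8: 3.0/9.8 = 30.6%. Event.
- 9.8 to 6.9: 2.9/9.8 = 29.6%. No criterion met.

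Since 6.9/0.70 = 9.86, all of this range escapes only for baselines below 8.57. Between 8.57 and about 9.9 the nadir decides, and above that every value in the range is already an event.

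**4. Conditions for a non-event.** The subject must be transfused before any criterion is met, have no missing haemoglobin to the cut-off, and meet no criterion at a later visit. With a missing value the endpoint is missing, and it is counted as haemolysis in Table 3.2.

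**5. Whether other displays pick it up.** The 8.2 to 6.2 fall is exactly 20 g/L. Figures 3.35-3.36 need more than 20 g/L. So does the profile plot (Figure 3.41), unless the subject is a female genotyped as deficient. The fall therefore sits in the lowest change category (RAP 8.2.2).

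**6. Effect of counting transfused subjects.** These use the RAP's Newcombe interval with assumed event counts out of 200 (tafenoquine) and 100 (primaquine). The difference is tafenoquine minus primaquine, in percentage points.

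| Observed events | After counting | Difference before (95% CI) | Difference after (95% CI) |
|---|---|---|---|
| 0 vs 0 | 2 vs 0 | 0.0 (−3.7 to 1.9) | 1.0 (−2.8 to 3.6) |
| 4 vs 1 | 6 vs 1 | 1.0 (−3.6 to 4.1) | 2.0 (−2.7 to 5.5) |
| 4 vs 1 | 4 vs 2 | 1.0 (−3.6 to 4.1) | 0.0 (−5.1 to 3.4) |
| 16 vs 8 | 18 vs 8 | 0.0 (−7.6 to 6.0) | 1.0 (−6.7 to 7.2) |

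One subject is 1/200 = 0.5 points or 1/100 = 1.0 point. With the 251 randomised (meta-analysis plan, section 3), split by assumption 167/84, it is 0.6 or 1.2 points.

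**The case against.** The haemoglobin-only definition is the protocol's own. The same criteria drive the haemoglobin stopping rule (6.4.2) and, in the first 15 days, the protocol-defined SAE (6.4.3.2). An objective laboratory endpoint is a legitimate choice, whereas a transfusion reflects a clinician's decision that varies by site. It may also reflect malaria itself: the wording "anemia (resulting in transfusion" in protocol 1.3.2 describes consequences of malaria episodes, especially in children, not drug haemolysis. Section 3.3.1 reports that the Phase II haemoglobin drops were considered disease-related. This stands, and it rules out replacing the primary endpoint.

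Nor are such subjects hidden. Table 3.55 counts transfusions, Table 3.20 reports haematologically related adverse events among the headline results, and protocol 6.4 requires clinically significant laboratory results to be recorded as adverse events. This also stands, but none of it shows how the primary estimate would change.

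A reader might infer that everyone transfused at 6.0-6.9 g/dL from a baseline of 7.0-9.8 g/dL is a non-event. The fall from 9.0 to 6.2 shows otherwise.

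A reader might also infer that donor blood distorts the maximum-fall displays and that post-transfusion values should be removed there. A raised value cannot be the largest fall. Removing later values could delete a real decline in a subject who kept falling despite transfusion.

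**Conclusion.** The point holds in a limited form. The RAP scores a transfused subject with complete data and no threshold value as not having haemolysis, and no primary or sensitivity analysis tests the effect. By the letter of the protocol's definition that subject is a non-event. The gap is that the endpoint cannot distinguish a subject who never approached a threshold from one held above it by donor blood.

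The direction is toward under-counting. The size cannot be estimated, since the documents give neither a transfusion trigger nor a frequency. The counts in the working are assumptions. In each scenario the shift from one or two subjects lies inside the original interval, so the documents do not support saying that the treatment comparison would be reversed or that events are known to have been lost. With few events expected, the shift could still be large relative to the point estimate. The change is worth making as an inexpensive improvement; it is not a correction of an invalid endpoint.

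**What to change.** - **Table 3.1.** Keep the haemoglobin-only endpoint as the primary row. Add a pre-specified supportive row, with the same Wilson and Newcombe intervals, that also counts a post-dose red-cell or whole-blood transfusion given for a fall in haemoglobin as an event. State how a transfused subject with missing haemoglobin is scored. Classify the reason for each transfusion before unblinding, as RAP 13.6.4 already does for concomitant medications.
- **Mean and categorical change from baseline (Tables 3.26, 3.28-3.29; Figures 3.38-3.39).** Flag post-transfusion haemoglobin values, or show the summary with and without them.
- **Maximum-fall and decline displays (Figures 3.35-3.37; Tables 3.30-3.31).** Leave unchanged.

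The cost is a paragraph in RAP 13.6.3 and 7.1.2 and a merge with transfusion data already planned for Table 3.55. The downside is that the supportive row includes a site-dependent clinical decision and may capture disease-related anaemia, which is why it is supportive only. No clinical rule is changed or proposed.

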13.6.4. Efficacy**Relapse free efficacy and Time to Relapse****Six months**

- A subject will be considered to have demonstrated relapse-free efficacy at 6 months for the purposes of the analysis if **all** of the following are true (also described in the flowchart below):
 - Subject had a non-zero *P. vivax* asexual parasite count at baseline. Subjects with no asexual *P. vivax* parasites at this time point will be censored with time to relapse = 0 days.
 - Subject demonstrated initial clearance of *P. vivax* parasitaemia. This is defined as two negative asexual *P. vivax* parasite counts, with at least 6 hours between the counts, and no positive counts in the interval. Subjects who do not meet this criteria will be classified as relapses, with time to relapse = 0 days.
 - Subject has no positive asexual *P. vivax* parasite count at any assessment prior to or on Study Day 201 following initial parasite clearance. Subjects who do have a positive count will be classified as relapses, with time to relapse = (date of first positive count) – (date of Study Day 1) days.
 - Subject did not take a concomitant medication with anti-malarial activity at any point between Study Day 1 and their last parasite assessment. A list of all concomitant medications will be reviewed by a GSK clinician prior to unblinding the study, and classified accordingly. Subjects who did take a drug with anti-malarial activity but never had a positive asexual *P. vivax* parasite count after initial clearance will be censored, with time to relapse censored at (date of last negative parasite assessment prior to concomitant medication start) – (date of Study Day 1). If a subject has not had a negative assessment prior to the concomitant medication start date, they will be censored at 0.
 - Subject is parasite-free at 6 months. This is defined as a negative asexual *P. vivax* parasite count at the first parasite assessment performed on or after Study Day 166.
- Subjects who do not have a positive asexual *P. vivax* parasite count following initial clearance but where the final parasite count occurred before Study Day 166 will not have been classified by the preceding rules. These subjects will be considered to be censored, with time to relapse censored at (Date of final parasite assessment) – (date of Study Day 1).
- If a subject has a relapse outcome and a censored outcome, they will be considered to be a relapse, even if the time point of the relapse is later than the time point of censoring. For example, a subject who took a medication with anti-malarial activity at Study Day 32, but remained parasite-free after initial clearance until Study Day 68 will be treated as a relapse at Study Day 68.

Relapse free efficacy and Time to Relapse

Flow chart of algorithm:

Four months

[figure not shown]
- A subject will be considered to have demonstrated relapse-free efficacy at 4 months for the purposes of the analysis if **all** of the following are true (also described in the flowchart below)::
 - Subject had a non-zero *P. vivax* asexual parasite count at baseline. Subjects with no asexual *P. vivax* parasites at this time point will be censored with time to relapse = 0 days.
 - Subject demonstrated initial clearance of *P. vivax* parasitaemia. This is defined as two negative asexual *P. vivax* parasite counts, with at least 6 hours between the counts, and no positive counts in the interval. Subjects who do not meet this criteria will be classified as relapses, with time to relapse = 0 days.
 - Subject has no positive asexual *P. vivax* parasite count at any assessment prior to or on Study Day 130 following initial parasite clearance. Subjects who do have a positive count will be classified as relapses, with time to relapse = (date of first positive count) – (date of Study Day 1) days.
 - Subject did not take a concomitant medication with anti-malarial activity at any point between Study Day 1 and their first parasite assessment after Study Day 109 (up to and including Study Day 130). A list of all concomitant medications will be reviewed by a GSK clinician prior to unblinding the study, and classified accordingly. Subjects who did take a drug with anti-malarial activity but never had a positive asexual *P. vivax* parasite count after initial clearance will be censored, with time to relapse censored at (date of last negative parasite assessment prior to concomitant medication start) – (date of Study Day 1). If a

Relapse free efficacy and Time to Relapse

subject has not had a negative assessment prior to the concomitant medication start date, they will be censored at 0.

- Subject is parasite-free at 4 months. This is defined as a negative asexual *P. vivax* parasite count at the first parasite assessment performed after Study Day 109 (up to and including Study Day 130).
- Subjects who do not have a positive asexual *P. vivax* parasite count following initial clearance but where the final parasite count occurred on or before Study Day 109 will not have been classified by the preceding rules. These subjects will be considered to be censored, with time to relapse censored at (Date of final parasite assessment) – (date of Study Day 1).
- If a subject has a relapse outcome and a censored outcome, they will be considered to be a relapse, even if the time point of the relapse is later than the time point of censoring. For example, a subject who took a medication with anti-malarial activity at Study Day 32, but remained parasite-free after initial clearance until Study Day 68 will be treated as a relapse at Study Day 68.

Flow chart of algorithm:

Relapse free efficacy at 6 months missing=failure definition

- In addition to those with a positive asexual *P. vivax* parasite count at any assessment prior to or on Study Day 201, the following subjects will also be defined to have relapsed:
 - Subject did not demonstrate initial clearance of *P. vivax* parasitaemia (i.e. did not have

Relapse free efficacy and Time to Relapse
 
two negative asexual P. vivax parasite counts, with at least 6 hours between the counts, and no positive counts in the interval)
 
 ○ Subject took a concomitant medication with anti-malarial activity at any point between Study Day 1 and their last parasite assessment. A list of all concomitant medications will be reviewed by a GSK clinician prior to unblinding the study, and classified accordingly. ○ Subject does not have a parasite assessment between Study Day 166 and 201. 
 ● Subjects with a zero P. vivax asexual parasite count at baseline will be excluded from the analysis.

Relapse free efficacy at 6 months missing on or after Day 29=failure definition
 
 ● In addition to those with a positive asexual P. vivax parasite count at any assessment prior to or on Study Day 201, the following subjects will also be defined to have relapsed: 
 ● Subject did not demonstrate initial clearance of P. vivax parasitaemia (i.e. did not have two negative asexual P. vivax parasite counts, with at least 6 hours between the counts, and no positive counts in the interval) ● Subject took a concomitant medication with anti-malarial activity at any point between Study Day 1 and their last parasite assessment. A list of all concomitant medications will be reviewed by a GSK clinician prior to unblinding the study, and classified accordingly. ● Subject with a missing parasite assessment on or after the Day 29 assessment ● Subjects with a zero P. vivax asexual parasite count at baseline will be excluded from the analysis.

Relapse free efficacy at 4 months missing=failure definition
 
 ● In addition to those with a positive asexual P. vivax parasite count at any assessment prior to or on Study Day 130, the following subjects will also be defined to have relapsed: 
 ○ Subject did not demonstrate initial clearance of P. vivax parasitaemia (i.e. did not have two negative asexual P. vivax parasite counts, with at least 6 hours between the counts, and no positive counts in the interval) ○ Subject took a concomitant medication with anti-malarial activity at any point between Study Day 1 and their last parasite assessment. A list of all concomitant medications will be reviewed by a GSK clinician prior to unblinding the study, and classified accordingly. ○ Subject does not have a parasite assessment between Study Day 110 and 130. ● Subjects with a zero P. vivax asexual parasite count at baseline will be excluded from the analysis.

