8.1.2. Planned Efficacy Statistical Analyses

Secondary Statistical Analyses
Endpoint(s)

 Relapse-free efficacy six months post-dosing Relapse-free efficacy four months post-dosing See Section 13.6.4 for derivations including censoring.
Model Specification

 Estimates for the relapse-free efficacy rate and time to relapse will be determined for each treatment group using the Kaplan-Meier method. Cox Proportional Hazards model with region and treatment as covariates will provide the hazard ratio mITT population

Secondary Statistical Analyses
Model Checking & Diagnostics

 Refer to Appendix 12: Model Checking and Diagnostics for Statistical Analyses.
Model Results Presentation

 Summary of the proportion of subjects with relapse-free efficacy by treatment group as n (%), including the sub-reasons for why subjects are not considered relapse-free defined in Section 13.6.4 (Table 2.5 for 6 months, Table 2.7 for 4 months). Note only the sub-reasons that apply to the population being displayed will be included. Analysis tables (Table 2.9 for 6 months, Table 2.11 for 4 months) will show: 
 Number of subjects with an observed relapse and numbers of subjects censored (censored prior to 6/4 months, and censored relapse-free at 6/4 months) Kaplan-Meier estimate and 95% confidence intervals of the relapse-free efficacy rate at 6/4 months for each treatment Kaplan-Meier quartile estimates and 95% confidence intervals of time to relapse Hazard ratio of TQ+CQ vs PQ+CQ over the first 6/4 months from Cox Proportional Hazards model 95% CI Kaplan-Meier survival curves will also be produced for 6 months (Figure 2.1).

Sensitivity and Supportive Statistical Analyses
1. Per Protocol population – Relapse free efficacy at 6 months and 4 months

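### Anti-malarial drug use censors a subject only if no relapse follows, so the Kaplan-Meier and Cox relapse analyses select on the later outcome; the size of the bias is unknown

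*Supplement*

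**What the plan says.** The current RAP (Amendment 1, February 2017) defines six-month time to relapse in section 13.6.4. For drugs with anti-malarial activity it makes two provisions.

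- No later positive smear: "Subjects who did take a drug with anti-malarial activity but never had a positive asexual" count after initial clearance "will be censored, with time to relapse censored at (date of last negative parasite assessment prior to concomitant medication start".
- A later positive smear: for subjects with both outcomes, "they will be considered to be a relapse, even if the time point of the relapse is later than the time point of censoring", with the later date as the event time. The worked example is "a subject who took a medication with anti-malarial activity at Study Day 32, but remained parasite-free after initial clearance until Study Day 68", who is an event at Day 68.

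The four-month definition in the same section and Meta-Analysis Plan section 8.2 carry the same two provisions.

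The variable feeds RAP section 8.1.2: "Estimates for the relapse-free efficacy rate and time to relapse will be determined for each treatment group using the Kaplan-Meier method", and "Cox Proportional Hazards model with region and treatment as covariates will provide the hazard ratio". In the Meta-Analysis Plan it feeds the pooled Cox model, whose upper 95% confidence bound is compared with a non-inferiority margin of 1.21 (section 9.4). Per Protocol is the primary population for that comparison (section 5).

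The Per Protocol definition in RAP section 13.1.1, criterion 6, removes subjects who took such a drug only if they also stayed smear-negative for the whole study.

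**The concern.** Take two subjects who start the same drug at Day 32. One is smear-positive at Day 68: that subject's time from Day 32 to Day 68 counts, and so does the event. The other never relapses and is removed at the last smear before Day 32. After drug use, person-time is kept only when it ends in an event. Kaplan-Meier and Cox both require that, at any time, staying under observation does not depend on what happens later. Here it does, by definition.

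At stake are the relapse-free rates reported for each arm and, if drug use is unequal, the hazard ratio. Efficacy is secondary in this study and untested, so the formal consequence lies in the meta-analysis, where the same variable is held against 1.21.

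**Working it through.** **Which censoring events matter.** Only drug use can precede a relapse. Censoring at the final smear cannot, and subjects with a zero baseline count fall outside mITT.

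**Direction, without simulation.** Kaplan-Meier is S = ∏(1 − d_j/n_j). Compare the RAP rule with following every taker to relapse or last smear. The events d_j and their times are identical. Under the RAP rule n_j is smaller, because non-relapsing takers have left. Each factor is no larger, so the RAP estimate can never exceed the follow-all estimate.

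**Hand example (illustrative).** 100 subjects; 10 take a drug at Day 32; 30% of takers (3) and 30% of the others (27) relapse at Day 68.

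| Rule | At risk at Day 68 | Events | Relapse-free |
|---|---|---|---|
| RAP | 100 − 7 = 93 | 30 | 1 − 30/93 = 67.7% |
| Censor all takers | 90 | 27 | 1 − 27/90 = 70.0% |
| Follow all takers | 100 | 30 | 1 − 30/100 = 70.0% |

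Both consistent rules return the true 70%.

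**Size under assumed drug use.** The documents give no rate, so large-sample simulation was used. Assumptions: scheduled smear visits to Day 180, constant relapse hazard after Day 32, drug start at a random time unrelated to relapse risk, no drug effect on relapse, and a true six-month relapse-free rate of 75%.

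| Assumed use | Kaplan-Meier bias |
|---|---|
| 2% | about −0.3 points |
| 5% | about −0.7 |
| 10% | about −1.4 (73.6% v 75.0%) |
| 20% | about −3 |

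If the drug halves the later relapse hazard, the shortfall against censoring all takers is smaller. Across 20 to 40% relapse, with 10% use, it is 0.7 to 1.1 points instead of 1.2 to 1.8.

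**Hazard ratio, TQ+CQ v PQ+CQ, true value 1, mITT.**

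| Assumed use, TQ v PQ | RAP rule | Either consistent rule |
|---|---|---|
| equal | 1.00 | 1.00 |
| 2% v 4% | 0.99 | 1.00 |
| 5% v 15% | 0.94 to 0.95 | 1.00 |
| 10% v 5% | 1.03 | 1.00 |

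**Against the margin.** The plan's margin reproduces as 1 + (1.84 − 1) × (1 − 0.75) = 1.21. On the log scale, 0.95 is ln(0.95)/ln(1.21) = −0.051/0.191, about a quarter of the margin.

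**Per Protocol.** Criterion 6 deletes non-relapsing takers altogether and keeps relapsing ones, so it makes the same selection. With 5% v 15% use, the Per Protocol hazard ratio is about 0.91. Changing only the censoring rule to censor-all leaves it at about 0.965. Both places must change.

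**The case against.** The strongest reply is that the trigger should be rare. A reader might infer from the breadth of protocol Appendix 5 (doxycycline, clindamycin, fluoroquinolones, co-trimoxazole, albendazole) that such use is common. The documents do not support that. Appendix 5 lists prohibited medicines, protocol section 5.6.2 bars them through Day 180, and section 5.6.1.1 limits allowable antibiotics to other classes. Use is a deviation, and which drugs count is settled by clinician review before unblinding. This stands: the rates above are assumptions, and at 2% use the effect is slight. With 251 randomised 2:1 (about 167 and 84), the 95% half-width of a 75% rate is 1.96 × √(0.75 × 0.25/n), or about 6.6 and 9.3 points.

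A reader might also infer that the hazard ratio is necessarily biased, or biased towards tafenoquine. Neither follows. With equal use it is unaffected, and with unequal use it can move either way. The trial is double-blind and double-dummy, and nothing in the documents predicts unequal use.

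A further reply is that planned sensitivity analyses cover this. The missing=failure analyses in RAP section 8.1.2 do count every drug taker as a failure whatever follows, which is an outcome-blind check. But they answer a composite question and do not repair the Kaplan-Meier or Cox results. In the Meta-Analysis Plan, the missing-on-or-after-Day-29 version is run only if proportional hazards fails. The logistic analysis that drops early-censored subjects removes only non-relapsing takers, so it selects in the same way.

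Lastly, censoring all takers discards confirmed relapses. That is a fair cost, and a reason to allow the follow-all rule as the main analysis instead.

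**Conclusion.** The defect is real and is in the current texts: whether a drug taker is censored is decided by the later outcome. The downward direction of the Kaplan-Meier bias relative to following everyone follows from the rule itself. Its size does not. It rests on assumed use rates, random timing and no drug effect, and runs from about 0.3 points at 2% use to about 3 points at 20%. The hazard ratio is distorted only if use differs by arm.

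It would be wrong to conclude that this study's main result is compromised. The primary endpoint is haemolysis, which the rule does not touch, and RAP section 2.4 states that no hypotheses are tested. The point matters most for the Per Protocol non-inferiority comparison, where two outcome-dependent rules act together. It should be fixed, because a rule that ignores the later outcome is available from the same data.

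**What to change.** 1. For drug use that starts before the first positive smear after clearance, apply one rule to every taker. Either censor all at the last negative smear before the drug, or follow all to relapse or last smear. Name one as the main analysis and the other as sensitivity. If the drug alters relapse risk, the two estimate different quantities, so the choice should be stated as such.
2. Keep as events all relapses that precede the drug, including those followed by rescue treatment.
3. Make the change together in the 6-month and 4-month definitions of RAP section 13.6.4 and in Meta-Analysis Plan section 8.2, and replace the Day 32/Day 68 example.
4. In RAP section 13.1.1, criterion 6, drop the condition on remaining smear-negative and handle these subjects by the same rule.
5. Report the number of takers by arm, with and without later relapse, so that readers can judge the size.

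Cost: wording in two plans, re-derivation and re-runs; no new data. Under censor-all, a few confirmed relapses move to the sensitivity analysis. The derivation shared with DETECTIVE Part 2 must be aligned; that study's own plan is not shown. The margin comes from DETECTIVE Part 1, so it should be checked whether that hazard ratio used the same rule.
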